**Document Date: 02/05/2017** 

## **Study Protocol**

The study was a single-blind randomized clinical trial with parallel group and allocation ratio was 1:1. This study was approved by the Clinical Research Institutional Review Board (No. 2017/53). The study was performed at the Department of Orthopaedics and Traumatology, Turgut Ozal Medical Hospital, Inonu University. Informed written consent was obtained from all participants' parents or legal guardians. The patients who met the inclusion criteria randomly assigned into two groups (Rehabilitation group, Mobilization group) in a ratio of 1:1 through the stratified block randomization method. The patients and the researcher who were responsible for the analyzing of the data were blinded to the randomization results. All data were collected at baseline, 1 week and 6 weeks (only quality of life).

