## **Statistical Analysis Plan**

The SPSS (version23; SPSSInc., Chicago, IL, USA) was used to conduct the analysis. Descriptive statistics were presented as mean  $\pm$  standard deviation and percentage. Suitability of variables to normal distribution were analyzed using visual (histogram and probability graphics) and analytical methods (Shapiro-Wilk Test). The differences between both groups were assessed by Chi-squared, Fisher's final test and independent sample t test. Split plot ANOVA was used to compare the pretreatment and posttreatment assessments at baseline, 1 week/6 week in both groups (group: rehabilitation vs mobilization; time: baseline vs 1 week/6 week). VAS, thorax mobility, trunk balance, 2MWT and SRS-22 scales were analyzed for both groups using the split plot ANOVA. A p value of <0.05 was considered to be significant.

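### The SAP does not say which SRS-22 visits enter the split plot ANOVA or which effect decides; a single baseline-adjusted 6-week comparison would settle this and usually gain power

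*Combined protocol and SAP*

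**What the plan says.** The Study Protocol section gives the schedule in one sentence: "All data were collected at baseline, 1 week and 6 weeks (only quality of life", where the bracket closes. On its plain reading, every outcome is taken at baseline and 1 week, and quality of life again at 6 weeks.

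The Statistical Analysis Plan section describes the model once for all outcomes: "Split plot ANOVA was used to compare the pretreatment and posttreatment assessments at baseline, 1 week/6 week in both groups", with the factors in brackets as "group: rehabilitation vs mobilization; time: baseline vs 1 week/6 week". It then lists the outcomes: "VAS, thorax mobility, trunk balance, 2MWT and SRS-22 scales were analyzed for both groups using the split plot ANOVA". The decision rule is "A p value of <0.05 was considered to be significant".

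For SRS-22 the plan does not state the number of levels of the time factor, whether the group-by-time interaction or a particular contrast decides, how sphericity would be handled with three levels, or whether two comparisons would share the 5%.

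**The concern.** SRS-22 is the only quality-of-life scale in the list of analysed outcomes, and quality of life is the only outcome carried past 1 week. The 6-week SRS-22 comparison is therefore the trial's only longer-term result. The slash in the time factor leaves at least three analyses open: one ANOVA with three time levels, two ANOVAs with two levels each, or one ANOVA of baseline against 6 weeks. They can give different p-values from the same data, and nothing in the plan chooses between them. If the choice is made after the data are seen, the nominal 5% no longer describes the SRS-22 result.

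A second issue does not depend on the slash. A two-level split plot interaction is a comparison of change scores. It gives up precision that adjustment for the baseline score would normally recover.

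**Working it through.** **Inputs.** From the documents: a 0.05 threshold, two groups with "parallel group and allocation ratio was 1:1", and visits at baseline, 1 week and 6 weeks. Not in the documents, hence assumed: two-sided tests, 15 to 30 patients per arm, the SDs, and the between-visit correlations r01 (baseline to 1 week), r06 (baseline to 6 weeks) and r16 (1 to 6 weeks). The plan has no figure of its own to reproduce.

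**1. Two separate two-level ANOVAs.**
- If the tests were independent, the chance of at least one false positive would be 1 − 0.95² = 0.0975.
- Both changes share the same baseline, so the tests are correlated. With equal SDs the correlation is ρ = (1 + r16 − r01 − r06) / [2√((1 − r01)(1 − r06))].
- All three correlations 0.5: ρ = 0.5/1.0 = 0.50, and the bivariate normal error is 0.091.
- r01 = r06 = 0.3, r16 = 0.8: ρ = 1.2/1.4 = 0.857, and the error is about 0.074.
- For reference, ρ = 0.8 gives 0.078 and ρ = 0.9 gives 0.070.
- Simulation (15 and 30 per arm, four covariance patterns, 20,000 runs each) gave 0.073-0.096.

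**2. One three-level ANOVA.** In the same simulations the uncorrected group-by-time F had error of 0.049-0.053 under compound symmetry and 0.055-0.067 under the three non-spherical patterns (mean estimated epsilon about 0.72-0.85). With the Greenhouse-Geisser correction it was 0.047-0.052 throughout.

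**3. One baseline-versus-6-week ANOVA.** The interaction has 1 df, its error is 0.05, and with two levels sphericity cannot fail. What remains is efficiency. Take equal SDs (set to 1) and write r for r06.
- Variance of the change score: 2(1 − r). Residual variance after baseline adjustment: 1 − r². Their ratio is 2/(1 + r).
- If the adjusted test has 80% power, its expected z is 1.960 + 0.842 = 2.802. The interaction's expected z is 2.802 × √((1 + r)/2).

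| r | Variance ratio | Expected z of interaction | Power of interaction |
|---|---|---|---|
| 0.3 | 1.40/0.91 = 1.54 | 2.802 × 0.806 = 2.259 | Φ(0.299) = 0.62 |
| 0.5 | 1.00/0.75 = 1.33 | 2.802 × 0.866 = 2.426 | Φ(0.466) = 0.68 |
| 0.6 | 0.80/0.64 = 1.25 | 2.802 × 0.894 = 2.506 | Φ(0.546) = 0.71 |

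Simulation at 25 per arm agrees: 0.602-0.709 for the interaction against 0.781-0.803 for ANCOVA at 6 weeks.

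**4. Condition on the gain.** With SDs s0 and s6, the change variance minus the adjusted variance is (s0² + s6² − 2r·s0·s6) − s6²(1 − r²) = (s0 − r·s6)². This is never negative, so adjustment does not lose beyond one degree of freedom. It is zero when s0 = r·s6, for example r = 0.5 with a 6-week SD twice the baseline SD. The gain is therefore expected but not guaranteed.

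**5. Three-level F against a 6-week test.**
- Against a baseline-versus-6-week interaction sized for 80% power: if the effect grows evenly (half at 1 week, compound symmetry), the F has 0.68-0.71 against 0.77-0.80. If the effect appears only at 6 weeks or is equal at both visits, the corrected F has about 0.80 or more against about 0.77-0.79, so it is not weaker.
- Against baseline-adjusted ANCOVA at 6 weeks (25 per arm, equal SDs, five correlation patterns): the corrected F had 0.421-0.776 against 0.781-0.803.

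**The case against.** The strongest reply is that the slash may be shorthand matched to outcome: baseline against 1 week for VAS, thorax mobility, trunk balance and 2MWT, and baseline against 6 weeks for SRS-22. The SAP speaks of pretreatment and posttreatment assessments and writes time as a pair, which fits. On that reading there is one SRS-22 test at 5%, with no second comparison and no sphericity assumption. This reading is possible, but the SAP does not state it, and the protocol sentence taken literally also has SRS-22 at 1 week.

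Second, a reader might infer that the plan contains no valid SRS-22 test. The documents do not support that. The baseline-versus-6-week interaction is one valid test, and so is the three-level interaction with an epsilon correction. The fault is that none is named.

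Third, a reader might infer that the three-level F is a weak test in general. It is not: whether it loses to the split plot 6-week contrast depends on how the effect develops over time. Its shortfall against ANCOVA comes partly from the lack of baseline adjustment, which is a separate matter from the ambiguous time factor.

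Fourth, all the sizes rest on assumed arm sizes, SDs and correlations, and neither section ranks 6 weeks above 1 week. Both points stand. The choice of 6 weeks as the deciding visit is a recommendation, based on its being the visit added for quality of life alone.

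**Conclusion.** The point holds as one of under-specification plus an avoidable loss of efficiency. The SRS-22 time factor and deciding effect are not fixed. Depending on what is run, the false-positive risk for SRS-22 is about 7-10% (two tests), about 5-6.7% (uncorrected three-level F), or 5% (baseline against 6 weeks only). It would be wrong to quote a figure near 10% as the plan's error rate: it applies to one reading only, and it falls towards 7% when the 1-week and 6-week scores are highly correlated.

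On efficiency, the baseline-versus-6-week interaction has about 60-71% power where the adjusted comparison has about 80%, at r = 0.3-0.6 and equal SDs. Put as sample size, it needs roughly 25-54% more patients for the same power (ratios 1.25 to 1.54). The benefit shrinks as r rises and can vanish if the SDs differ in the particular way shown above. This is worth changing because it is cheap and helps even if the single-test reading is the intended one. It does not address the wider gap that none of the five scales is named as primary.

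**What to change.** - State the SRS-22 visits in the same words in the Study Protocol and Statistical Analysis Plan sections, including whether SRS-22 is taken at 1 week.
- Make the group difference in SRS-22 at 6 weeks, adjusted for baseline SRS-22 by ANCOVA and reported with its 95% CI, the single SRS-22 test. Treat any 1-week SRS-22 result as supportive.
- If SRS-22 is taken at 1 week, a mixed model for the 1-week and 6-week scores is an acceptable equivalent. It would have baseline as covariate, terms for group, visit and group-by-visit, and unstructured covariance, with the 6-week group difference as the deciding contrast.
- If the three-level split plot ANOVA is kept, name the group-by-time interaction as the deciding effect and report its Greenhouse-Geisser-corrected result.

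The cost is a few sentences in the SAP and a procedure available in the stated software, with no new data, visits or patients. The downside is that the 1-week SRS-22 result can no longer be claimed as a separate significant finding.
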